15.2. Schedule of DMC Reviews

Table 15-2 Schedule of DMC Reviews

		Milestone *
Part 1	Teleconference	75 patients (60%)
	Face to face	IA-120 patients
Part 1-Electronic Reviews		25 patients
		50 patients
		100 patients
Part 1 – Ad hoc Review		Between 90 and 120 Patients
Part 2	Teleconference	60 additional patients in Part 2 patients (at least 180 total)
	Teleconference	125 additional patients in Part 2 patients (at least 245 total)
Part 2-Electronic Reviews		30 additional patients in Part 2 patients (at least 150 total)
		90 additional patients in Part 2 patients (at least 210 total)
Part 2-Ad hoc Review		Between 125 and 170 patients in Part 2 (at least 245-290 total)

* Milestone refers to patients with at least 7 days of laboratory data, allowing for patients that were randomized but discontinued/died prior to 7 days

15.3. Weight Ranges and Pre-calculated Corresponding Volumes

Table 15-3 Weight Ranges and Pre-calculated Corresponding Volumes

Body weight (kg)	Body weight (lb)	Volume drawn from 4 vials (mL)	Volume discarded from syringe (mL)	IMP retained in syringe (mL)	Saline added to reconstitute (mL)	Total volume in syringe (mL)
35 < 40	77 < 88	20	12	8	42	50
40 < 45	88 < 99	20	11	9	41	50
45 < 50	99 < 110	20	10	10	40	50
50 < 55	110 < 121	20	9	11	39	50
55 < 60	121 < 132	20	8	12	38	50
60 < 65	132 < 143	20	7	13	37	50
65 < 70	143 < 154	20	6	14	36	50
70 < 75	154 < 165	20	5	15	35	50
75 < 80	165 < 176	20	4	16	34	50
80 < 85	176 < 187	20	3	17	33	50
85 < 90	187 < 198	20	2	18	32	50
90 < 95	198 < 209	20	1	19	31	50
95 - 115	209 < 253	20	0	20	30	50

Abbreviation: I

IMP = investigational medical product.

In line with [Table 15-3](#), the volume of investigational product (mL) administered to each patient is defined for a range of body weights – hence, the dose (mg/kg) can vary slightly dependent on where a patient lies within a weight range, even if the infusion is prepared correctly. The investigation product has a concentration of 8 mg/mL, thus the exact dose is calculated as

$$\frac{5 \times \text{IMP retained in syringe (mL)} \times \text{Treatment group}}{\text{Weight (kg)}}$$

where Treatment group = 0.4, 0.8, and 1.6 respectively for the recAP groups. The minimum doses for a correctly prepared infusion (corresponding to the maximum weight within each range in [Table 15-3](#)) are 0.4 mg/kg, 0.8 mg/kg and 1.6 mg/kg respectively for each of the recAP treatment groups. The maximum doses (corresponding to a patient with body weight 35 kg) are 0.457 mg/kg, 0.914 mg/kg and 1.829 mg/kg respectively.

Therefore, the dose windows in Section 4 used to assign patients to received treatment group based on average dose are based on the average midpoints between the minimum and maximum possible doses of each weight group for each treatment group (0.62 mg/kg for the split between the 0.4 mg/kg and 0.8 mg/kg groups; and 1.23 mg/kg as the cutoff between the 0.8 mg/kg and 1.6 mg/kg groups).

15.4. GFR formula

Based on this CKD-EPI formula the glomerular filtration rate (eGFR) is calculated based on the serum creatinine value as:

$$\text{GFR} = 141 \times \min(S_{\text{cr}}/\kappa, 1)^{\alpha} \times \max(S_{\text{cr}}/\kappa, 1)^{-1.209} \times 0.993^{\text{Age}} \times 1.018 \text{ [if female]} \times 1.159 \text{ [if black]}$$

where:

S_{cr} is serum creatinine in mg/dL,

κ is 0.7 for females and 0.9 for males,

α is -0.329 for females and -0.411 for males,

min indicates the minimum of S_{cr}/κ or 1, and

max indicates the maximum of S_{cr}/κ or 1.

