8.1. Primary Efficacy Endpoint

The primary endpoint will be calculated from standardized endogenous creatinine clearance measurements on Day 1 (first measurement after treatment) to Day 7, inclusive. Standardized endogenous creatinine clearance is assessed on each day during a 6 ± 1 hour period and calculated in mL/min as the mean creatinine clearance over the period, which is expected to be representative of the full 24 hours for that day.

An adjudication committee will review the standardized endogenous creatinine clearance data on a case-by-case basis to determine the values to be used in the analysis and for the derivation of AUC_{1-7} (see [Section 8.1.2](#)). The standardized endogenous creatinine clearance (mL/min) will be calculated by PPD Biostatistics using the following formula.

$$\frac{\text{Urine Creatinine (mg/dL)}}{\text{Serum Creatinine (mg/dL)}} \times \frac{\text{Total urine volume collected (mL)}}{\text{Stop date/time} - \text{Start date/time of urine collection (min)}}$$

- The urine creatinine (mg/dL) and serum creatinine (mg/dL) assessed by the central laboratory will be used to determine the standardized endogenous creatinine clearance.
- Per protocol, two blood samples are collected to evaluate the serum creatinine, one at the beginning of the urine sample collection and the other at the end of the urine sample collection. The average of these two serum creatinine measurements will be used in the formula above to assess the standardized endogenous creatinine clearance. In case there is only one serum creatinine sample available, then the serum creatinine concentration from that one sample will be used in the formula.
- The number of minutes from the start date/time to the stop date/time of urine sample collection and the total urine volume (mL) will be derived from the Urine Volume eCRF page. If the urine volume is recorded as 0 mL, then the standardized creatinine clearance will be 0 mL/min and will not be set to missing. If the urine volume is not recorded as missing but the volume is less than 30mL/24 hrs, then the standardized creatinine clearance will be set to 1 mL/min.

The adjudicated Part 2 data will be used to determine the AUC_{1-7} (primary endpoint), while the adjudicated Part 1 data will be used in a sensitivity analysis of the primary endpoint (as described in section 8.1.4). All data will be listed.

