Kidney function will be assessed at Baseline, Day 14, 21 and 28 by measured creatinine clearance. Baseline kidney function will only be measured by standardized creatinine clearance, however for Day 14, 21 and 28 summaries if creatinine clearance is not available then kidney function as assessed by eGFR (estimated by the CKD-EPI formula based on serum creatinine) will be used.. Kidney function will also be assessed at Day 60 and Day 90 by eGFR. Sustained loss of Kidney function, defined by eGFR < 60 mL/min, will be assessed at Day 60 and Day 90. The analyses of kidney function and sustained loss of kidney function at each timepoint will exclude any patients who die prior to the timepoint. Any other missing assessments (including early withdrawals) at Day 60 or Day 90 will be imputed by LOCF where possible, missing Day 14, 21 and 28 values will not be imputed and will be treated as missing. A summary table will present descriptive statistics for the reference kidney function and the kidney function at Baseline and at Days 14, 21, 28, 60 and 90 along with counts and percentages of patients with loss of sustained kidney function at Day 60 and Day 90. Descriptive statistics will also be presented for the change from baseline creatinine clearance value at Day 14, Day 21, Day 28, Day 60, and Day 90.

The absolute difference between placebo and each of the treatment groups will also be presented at each time point. Summaries for Day 60 and 90 will be repeated with and without the LOCF imputation of missing values applied.

All kidney function data will be listed.

Dialysis Dependency

Incidence of dialysis dependency will be assessed at Day 60 and Day 90. Patients who die or withdraw from the study prior to Day 60 or Day 90, respectively, without recording incidence of chronic dialysis will be counted as not being dialysis dependent. A summary table will present the counts and percentages of patients who are dialysis dependent at Day 60 and Day 90. Percentages for each timepoint are calculated based on the number of patients that were assessed including those who died or withdrew prior to timepoint.

All data on dialysis dependency will be listed.

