8.3. Other Efficacy Endpoints

Composite Endpoints

Patients that meet, or do not meet at least 1 of the following criteria will be summarized by counts and percentages for each composite endpoint:

Composite Endpoint 1:

1. Received RRT (prior to Day 28 [inclusive]) or
2. Died (prior to Day 28 [inclusive])

Composite Endpoint 2:

1. eGFR < 60 mL/min (at Day 60, estimated by the CKD-EPI formula based on serum creatinine) or
2. Dialysis dependency (up to Day 60) or
3. Died (prior to Day 60)

Composite Endpoint 3:

1. eGFR < 60 mL/min (at Day 90, estimated by the CKD-EPI formula based on serum creatinine) or
2. Dialysis dependency (up to Day 90) or
3. Hospitalized for a new episode of AKI (prior to Day 90) or
4. Died (prior to Day 90)

Exploratory analysis of each composite endpoint will be undertaken for the comparison of the optimal recAP dose and placebo using a logistic regression model with treatment group and site as explanatory variables. The odds ratio and associated 95% confidence interval from the comparisons of the optimal recAP dose versus Placebo will be presented together with the p-value for this comparison.

Serology

Serology is assessed by IgG, IgE, and total immunoglobulin at Baseline, Day 14 and Day 28.

The observed values and change from baseline for IgG, IgE, and total immunoglobulin will be calculated by visit and summarized with descriptive statistics.

All Serology data will be listed.

Anti-Drug Antibody Data

All anti-drug antibody data will be listed.

Quality of Life

Quality of Life is assessed by the EQ-5D questionnaire at Baseline, ICU/Intermediate care discharge, and Day 90.

The questionnaire assesses 5 dimensions: mobility, self-care, usual activities, pain/discomfort and anxiety/depression. Each dimension has 5 response options (no problems, slight problems, moderate problems, severe problems, and extreme problems) that reflect increasing levels of difficulty. The patient will be asked to indicate his/her current health state by selecting the most appropriate level in each of the 5 dimensions.

The questionnaire also includes a visual analogue scale, where the patient will be asked to rate current health status on a scale of 0-100, with 0 being the worst imaginable health state.

The EQ-5D responses from each dimension will be summarized with counts and percentages by treatment group and visit.

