Iohexol plasma concentrations will be listed and summarized using descriptive statistics by timepoints. Iohexol PK parameters will be listed and summarized using descriptive statistics. These summaries will include the number of patients (n), mean, standard deviation (SD), coefficient of variation (CV), minimum, median, maximum, geometric mean, and geometric %CV, when applicable.

Iohexol clearance ($CL_{Iohexol}$), as a gold standard measure of GFR, will be correlated to creatinine clearance in a subset of patients using scatter plots.

Exogenous Creatinine Clearance

To evaluate if renal replacement therapy (RRT) has an effect on endogenous creatinine clearance, the exogenous creatinine clearance by RRT equipment will be assessed by measuring the creatinine concentration in the effluent and effluent volume during the 6 ± 1 hour urine collection interval. This will be only done by the sites participating in the Iohexol substudy.

Standardized exogenous creatinine clearance (mL/min) by the RRT equipment will be calculated by PPD Biostatistics using the following formula.

$$\frac{\text{Effluent Creatinine (mg/dL)}}{\text{Serum Creatinine (mg/dL)}} \times \frac{\text{Total effluent volume collected (mL)}}{\text{Stop date/time – Start date/time of effluent collection (min)}}$$

- The effluent creatinine (mg/dL) will be assessed by the laboratory conducting the Iohexol data.
- The serum creatinine (mg/dL) assessed by the central laboratory and used in the primary endpoint of endogenous creatinine clearance will be used to determine the standardized exogenous creatinine clearance.
- Per protocol, two blood samples are collected to evaluate the serum creatinine, one at the beginning of the urine sample collection and the other at the end of the urine sample collection. The average of these two serum creatinine measurements will be used in the formula above to assess the standardized exogenous creatinine clearance. In case there is only one serum creatinine sample available, then the serum creatinine concentration from that one sample will be used in the formula.
- The number of minutes from the start date/time to the stop date/time of effluent sample collection and the total effluent volume (mL) from the RRT equipment will be derived from data collected at site.

The time-corrected exogenous creatinine clearance will be listed for subjects who are on RRT in the Iohexol population.

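### Day 60/90 eGFR and sustained loss, and the Day 14–28 eGFR fallback, have no rule for patients on dialysis, so their kidney function may be overstated

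*SAP*

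**What the plan says.** SAP section 15.4 gives the estimator: "the glomerular filtration rate (eGFR) is calculated based on the serum creatinine value", by a CKD-EPI equation whose other terms are age, sex and race. It has no term or exception for RRT.

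SAP section 8.2.2.1 (Kidney function) uses it in three places:

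- Days 60 and 90: "Kidney function will also be assessed at Day 60 and Day 90 by eGFR", with no other measure.
- Sustained loss: "Sustained loss of Kidney function, defined by eGFR < 60 mL/min, will be assessed at Day 60 and Day 90".
- Days 14, 21 and 28: measured urinary creatinine clearance comes first, but "if creatinine clearance is not available then kidney function as assessed by eGFR" takes its place.

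That section drops patients who died before the time point and fills other Day 60/90 gaps by last observation carried forward (LOCF). Gaps at Days 14–28 stay missing. Neither step looks at RRT status. Protocol section 7.3.1 defines Day 60/90 kidney function and sustained loss the same way and also removes only deaths.

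Dialysis dependency at Days 60 and 90 is a separate endpoint in SAP 8.2.2.1. It also enters the composites in SAP section 8.3: composite 2 is met by eGFR below 60 mL/min, "Dialysis dependency (up to Day 60) or" death. Composite 3 has the matching component up to Day 90.

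**The concern.** Protocol section 3.1.1 gives new or worsening chronic kidney disease as the reason for following patients to Day 90, and protocol section 4.1.2 keeps out patients with a known sustained eGFR below 60. Day 60/90 eGFR is therefore the direct reading on that question.

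In a patient on dialysis, the machine partly sets the serum creatinine. The equation then credits the patient's own kidneys with clearance that the machine supplied. Followed as written, the rule returns a value for these patients that need not describe their kidneys.

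Two things are at stake. The eGFR summaries can overstate function by an amount that grows with the share of patients dialysed. If the arms differ in dialysis, this pulls the eGFR difference caused by dialysis towards zero. And a patient can fail composite 3 because of dialysis while being counted at the same visit as having no sustained loss.

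**Working it through.** The plan states no eGFR figure for patients on RRT, so there is none to reproduce. As a unit check, the SAP Table 4-2 factor gives 150 µmol/L × 0.0113122 = 1.697 mg/dL, matching the 1.70 in protocol section 4.1.2.

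**Inputs.** The equation is from SAP 15.4. The RRT stopping criteria are from protocol section 6.3.9: continue at own clearance of 12 mL/min or less, physician's decision between 12 and 20, discontinue at 20 or more. Creatinine in patients on RRT at Days 14–90 is not given; I assume a range of 0.8 to 8 mg/dL.

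**Step 1: the formula.** eGFR = 141 × min(S/κ, 1)^α × max(S/κ, 1)^(−1.209) × 0.993^age, times 1.018 if female and 1.159 if black, with S in mg/dL. For a non-black man aged 65 with S = 2.0: S/κ = 2.0/0.9 = 2.222; 2.222^(−1.209) = 0.381; 0.993^65 = 0.633; eGFR = 141 × 0.381 × 0.633 = 34.0.

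| Creatinine (mg/dL) | eGFR, man 65 | eGFR, woman 65 |
|---|---|---|
| 0.8 | 93.7 | 77.4 |
| 1.0 | 78.6 | 59.1 |
| 1.5 | 48.2 | 36.2 |
| 2.0 | 34.0 | 25.6 |
| 3.0 | 20.8 | 15.7 |
| 4.0 | 14.7 | 11.1 |
| 6.0 | 9.0 | 6.8 |
| 8.0 | 6.4 | 4.8 |

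**Step 2: against the RRT criteria.** At age 65, eGFR is 20 or more whenever creatinine is at or below 3.10 mg/dL (man) or 2.45 (woman). It is above 12 whenever creatinine is below about 4.7 (man) or 3.7 (woman). Over those ranges, the score exceeds the own clearance at which the protocol stops RRT, or continues it, respectively.

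**Step 3: the sustained-loss cut-off.** Setting eGFR to 60 and solving gives S = κ × (141 × 0.993^age × sex factor / 60)^(1/1.209).

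- Man aged 60: 141 × 0.656 / 60 = 1.542; 1.542^(1/1.209) = 1.431; × 0.9 = 1.29 mg/dL.
- Woman aged 60: 141 × 0.656 × 1.018 / 60 = 1.569; 1.569^(1/1.209) = 1.452; × 0.7 = 1.02 mg/dL.
- Ages 18 to 85: 1.64 down to 1.11 (men), 1.30 down to 0.88 (women). With the race factor the highest value is about 1.85.

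A dialysed patient with creatinine above about 1.9 mg/dL is therefore always classed as sustained loss; misclassification is possible only below these cut-offs.

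**Step 4: are such values reachable? (Assumed inputs.)** Take 75 kg, no own clearance, continuous machine clearance K of 20–40 mL/min and creatinine generation G of 8–20 mg/kg/day. Steady-state creatinine is G × 75 / 1440 / K × 100. The extremes are 8 × 75 / 1440 / 40 × 100 = 1.04 and 20 × 75 / 1440 / 20 × 100 = 5.21 mg/dL. These give eGFR 74.8 to 10.7 (man aged 65) or 56.2 to 8.0 (woman aged 65). Moderate values are reachable, values above 60 occur only at the extreme, and none reaches 90. Intermittent dialysis is not at steady state, so this is an illustration only.

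**Step 5: arm means (assumed share).** The shift is the share dialysed × (eGFR − own clearance). With eGFR 34, the excess is 34 − 12 = 22 at own clearance 12, and 34 − 20 = 14 at own clearance 20. For assumed shares of 2% to 10%, the arm mean rises by 0.3 to 1.4 mL/min (excess 14) or 0.4 to 2.2 mL/min (excess 22). The documents give neither the share nor the creatinine, so this is not an estimate for the trial.

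**The case against.** The case on the other side is substantial, and most of it stands as a limit on the point.

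- **Days 14–28 are mostly covered.** A reader might infer that all kidney function from Day 14 to Day 90 rests on CKD-EPI. It does not: measured clearance has priority, and for zero urine SAP section 8.1 says "the standardized creatinine clearance will be 0 mL/min and will not be set to missing". The gap is the fallback, used when urine cannot be collected reliably. Protocol 6.3.9 allows intermittent dialysis from Day 8, so a patient on RRT can fall into it.
- **Normal eGFR is not shown.** A reader might infer that dialysed patients are scored as moderate or normal. The documents give no creatinine on RRT. At age 65, an eGFR of 90 needs creatinine of about 0.88 (man) or 0.71 mg/dL (woman) or lower, and many plausible values give an eGFR below 30.
- **Benefit or harm is not hidden.** Dialysis dependency is summarised by arm. Composites 2 and 3 count it as failure and receive the odds ratio, interval and p-value. Kidney function and sustained loss are only described. RRT incidence is itself the key secondary endpoint.
- **Failing a composite but not one component is ordinary.** True, but here the split comes from a creatinine the machine has lowered, not from a difference in kidney function.
- **LOCF is partly checked.** SAP 8.2.2.1 repeats the Day 60/90 summaries without LOCF. That does not help when the observed sample was itself taken on dialysis.
- **Assigning 0 mL/min has its own bias.** Protocol 6.3.9 allows RRT to continue with own clearance up to just under 20, so 0 can be further from the truth than the eGFR it replaces. This stands, and limits the remedy.

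The separate reporting of dialysis does not correct the eGFR means or the sustained-loss counts, and nothing in either document supplies the missing rule.

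**Conclusion.** The point holds in a limited form. For Day 60/90 eGFR, sustained loss, the Day 14–28 fallback and LOCF, neither document says what to do with a patient on RRT, and the rule as written treats a dialysis-lowered creatinine as native function.

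The continuous summaries are the more exposed. Under the equation, any creatinine below about 4.7 mg/dL (man aged 65) or 3.7 (woman aged 65) scores above the own clearance at which the protocol continues RRT. Investigators may depart from those RRT criteria, so 12 and 20 mL/min are reference points, not bounds for every patient. The binary endpoint is exposed only below roughly 0.9 to 1.6 mg/dL, depending on age and sex, or up to about 1.85 with the race factor.

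The size in this trial cannot be determined from the documents. It should not be read as an error in the equation, or as a threat to the primary or key secondary endpoint. These are exploratory endpoints, and the point deserves correction because they address the stated purpose of the 90-day follow-up.

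**What to change.** In SAP section 8.2.2.1, with a cross-reference from section 15.4:

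1. Count recorded dialysis dependency at Day 60 or Day 90 as sustained loss, in line with composites 2 and 3. Record this in SAP section 12 as a change from the protocol 7.3.1 definition.
2. Do not compute a CKD-EPI eGFR from a sample taken on RRT, or at a visit where dialysis dependency is recorded. Do not carry such a value forward by LOCF, and do not fill the gap it leaves with an earlier value.
3. Show the number of such patients by arm beside each eGFR summary. Add a sensitivity analysis that assigns them a low value and reports medians beside means. Keep the assigned value out of the main summary.

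The data are already collected: RRT start and stop dates to Day 28, and dialysis dependency at Days 60 and 90. The work is SAP wording and one derivation. The costs are a small departure from the protocol definition and fewer patients in the eGFR means. Those means would then describe patients off dialysis only, which is why the counts by arm must sit beside them.
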